## DESIGN AND METHODS

Our **specific hypothesis** is that the consumption of 2 Hayward green kiwifruit (containing actinidin protease) prior to 100g of ground beef will increase the rate of protein digestion from the beef in the elderly, leading to an increased uptake of the essential amino acids. Furthermore, this increased essential amino acid availability will produce a greater postprandial net anabolic protein response, as well as increased fractional synthetic rates of muscle and liver proteins.

To test this hypothesis we will use a double-blinded crossover design involving two intervention arms; in both arms 100g of ground beef (cooked weight) will be consumed following either 2 Hayward green kiwifruit (containing actinidin protease) or 2 Hort16A Gold kiwifruit (devoid of actinidin protease) by elderly subjects.

In response to the interventions, our primary endpoints are:

- the rate of beef protein digestion in the stomach (7);
- plasma amino acids (AA) which will reflect dietary digestibility and availability of precursors for protein synthesis (1);
- the magnitude of the whole-body net anabolic response (NAR), defined as the difference between whole body protein synthesis and protein breakdown, to determine overall protein balance, accounting for all roles of protein in the body (4, 13);

[figure not shown]
and our secondary endpoints are:

- the muscle fractional synthetic rate (FSR) on muscle protein synthesis (4, 13);
- the fibrinogen FSR to determine the impact of actinidin-assisted protein digestion on liver protein synthesis ([name], unpublished research);
- plasma glucose and insulin which will reflect the wider metabolic response (12).

These endpoints will enable achievement of the four objectives summarised in Table 1 on the second page of this proposal.

#### **Experimental Overview and Rationale:**

We will study a total of 15 healthy male and females between 60 and 85 years of age in a doubleblinded crossover design composed of two intervention arms, as detailed in Figure 3. With a sample size of N=15 subjects, the crossover design will have 80% power to detect a significant effect, where statistical significance is set at p<0.05. The 60-85 year age group was chosen due to the significant loss of muscle mass apparent at this stage of aging, which will provide a backdrop for the most pronounced effects and thus most scientifically accurate measurements. The entire study will take place at University of Arkansas for Medical Sciences (UAMS), in collaboration with [name]. [name] is an international expert in the use of stable isotope tracer technology for the measurement of protein metabolism and developed a majority of the methods considered to be gold-standard for this work. As this is a clinical study with complex methodology, completion of the experimental portion at UAMS under the supervision of [name] and his highly experienced team, will ensure that all procedures are conducted in the manner required for maximum accuracy and sensitivity of the data.

**Figure 3.** Complete outline of crossover design showing phases of study for a subject undergoing treatment A first and treatment B second.

Study Interventions. The interventions are as follows:

- A. 100g of ground beef plus 2x Hort 16A Gold kiwifruit (Control)
- B. 100g of ground beef plus 2x Hayward Green kiwifruit

The studies are referred to as Study A and Study B, respectively, in Figure 3. These amounts were chosen because 100g beef is the recommended serving size of beef for the elderly and we know from previous work that 100g of beef will induce a robust anabolic response (5, 6). Two Hayward Green, but not Hort16A Gold, kiwifruit had a significant effect on the rate of digestion of beef protein in pig trials (7). Ground beef will be produced to have an average protein composition of 25% (10); as 35g of protein is likely to saturate the muscle synthetic response, 25g will be within the range that permits detection of a difference in muscle protein synthetic rate between interventions. The use of ground beef will also limit any effects of masticatory differences between individuals. Subjects will also be selected to ensure masticatory function has not deteriorated.

Each subject will undergo both interventions, eating either Hort16A Gold fruit for the first arm and Hayward Green fruit for the second arm, or vice versa. Neither subjects nor meal distributors will be informed as to which kiwifruit variety contains actinidin; the study is therefore double-blinded.

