### Experimental Details:

Participant Selection and Screening: We will study a total of 15 healthy male and females between 60 and 85 years of age. Subjects will not participate in any organized exercise program, or perform any strenuous exercise 72 hours prior to the metabolic experiment.

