value for phenylalanine to protein based on the assumption that contribution of phenylalanine to protein is 4% (100/4 = 25) (2). PRO is the amount of exogenous protein (g) that is the amount of amino acids appearing in the circulation as a result of the exogenous protein digestion, accounting for splanchnic extraction (29%) of amino acids in young adults (11). Phe hydroxylation rate is the rate of appearance of tyrosine derived from phenylalanine through process of hydroxylation. Calculation of muscle protein FSR will be performed as previously described (5, 6).  $E_{BP1}$  and  $E_{BP2}$  are the enrichments of protein bound L-[*ring*-H5]-phenylalanine in the first and second muscle biopsies, respectively, and  $E_m$  is the mean plasma enrichment of the L-[*ring*-H5]-phenylalanine. *t* is the duration of time in minutes elapsed between two muscle biopsies; 60 and 100 are factors used to express muscle protein synthesis in percent per hour.

Statistical analysis and power calculations. Where effects of both the intervention and time require analysis, a two-way analysis of variance (ANOVA) model with repeated measures will be used. When significant differences between the interventions were identified by ANOVA, post-hoc Student's t-tests will be performed. When analysis involves the comparison of the total response to each intervention only, paired student's t-tests will be used. For all comparisons, statistical significance will be set at p < 0.05.

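### The stated 80% power holds only if all 15 subjects supply both study days, and the planned repeated-measures ANOVA has no rule for an incomplete time course

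*Combined protocol and SAP*

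**What the plan says.** The power statement is in the Experimental Overview and Rationale: "With a sample size of N=15 subjects, the crossover design will have 80% power to detect a significant effect". The section on participant selection and screening repeats the same number as the total: "We will study a total of 15 healthy male and females between 60 and 85 years of age". The overview section also says that every subject receives both interventions, and a two-week washout separates the arms.

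The analysis paragraph, headed "Statistical analysis and power calculations", names two main methods. Where both intervention and time are of interest, "a two-way analysis of variance (ANOVA) model with repeated measures will be used", followed by post-hoc t-tests. Otherwise: "When analysis involves the comparison of the total response to each intervention only, paired student's t-tests will be used". The significance level is common to all: "For all comparisons, statistical significance will be set at p < 0.05".

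Each study day has 15 blood samples (4 fasted and 11 fed) and three muscle biopsies. Whole-body kinetics are calculated from the AUC of plasma enrichment. Muscle FSR is calculated from two biopsies and a mean plasma enrichment. The documents do not mention withdrawals, replacement, imputation or missing samples, and they give no endpoint, effect size or SD for the 80%.

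**The concern.** The number to be studied and the number that gives 80% power are the same, so there is no margin. Each subject, aged 60 to 85, is asked for two 9.5-hour infusion days, six biopsies (2 × 3) and 30 blood samples (2 × 15), with a washout in between. Some loss is plausible, and the plan does not say what happens when it occurs.

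Two different losses matter.

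- **A subject without a second study day** provides no paired difference and drops out of every paired t-test. Power falls below the stated figure.
- **A subject with both study days but a missing blood sample** has an incomplete time course. The classical two-way repeated-measures ANOVA works on a full subject-by-intervention-by-time table. The analyst must then delete the subject, with the other samples from both days, or fill the gap by a method chosen after the data are seen.

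At stake are a power statement that is a best case without saying so, and time-course data obtained at real burden that the chosen method may discard.

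**Working it through.** **Inputs from the documents.** N = 15, power 80% and significance level 0.05 (Experimental Overview and Rationale; Statistical analysis and power calculations). Paired t-test for total responses (same analysis paragraph).

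**Inputs not in the documents.** The test is assumed two-sided. The standardised paired difference d (mean difference divided by the SD of the differences) is back-solved from the 80%. Loss rates and within-subject correlations below are assumptions.

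**Step 1: reproduce the 80%.** It cannot be reproduced forwards, because no effect size or SD is given. Power of a paired t-test with n pairs is P(T > t_crit), where T follows a noncentral t distribution with n − 1 degrees of freedom and noncentrality d√n. The opposite tail is negligible. Setting power to 0.80 at n = 15 gives d = 0.778: t_crit = 2.145, noncentrality 0.778 × √15 = 3.013, power 80.0%.

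**Step 2: hold d at 0.778 and reduce the complete pairs.**

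| Complete pairs | t_crit | d√n | Power |
|---|---|---|---|
| 15 | 2.145 | 3.013 | 80.0% |
| 14 | 2.160 | 2.911 | 76.8% |
| 13 | 2.179 | 2.805 | 73.1% |
| 12 | 2.201 | 2.695 | 69.0% |
| 11 | 2.228 | 2.580 | 64.4% |

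**Step 3: sensitivity to the form of the test.** Each variant is re-solved to 80% at 15 pairs.

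| Variant | d | 14 pairs | 13 pairs | 12 pairs |
|---|---|---|---|---|
| Two-sided paired t | 0.778 | 76.8% | 73.1% | 69.0% |
| One-sided paired t | 0.676 | 77.3% | 74.2% | 70.8% |
| Two-sided normal approximation | 0.723 | 77.2% | 74.2% | 70.7% |
| Period-adjusted (n − 2 df) | 0.783 | 76.7% | 72.9% | 68.6% |

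One lost pair costs about 3 points in every variant. Three cost about 9 to 11.

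**Step 4: how likely is a loss (illustrative).** With an independent loss probability p per subject, the chance of at least one loss is 1 − (1 − p)^15. At p = 5%, 10% and 20% this is 54%, 79% and 96%. Averaging the two-sided paired-t power over the binomial number of completers gives 77.5%, 74.7% and 68.4%.

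**Step 5: which analyses a missed draw touches.** Net balance rests on an AUC, and muscle FSR on two biopsies and a mean enrichment. Each is one summary per subject and period, which can usually still be formed with one sample missing, at some loss of precision. The complete-table requirement bites only where intervention and time are analysed together by the ANOVA.

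**Step 6: what a mixed model recovers after withdrawal.** Take 13 complete pairs plus two visit-1-only subjects, one on each fruit, with common variance, within-subject correlation ρ and no period effect. The information on the difference is proportional to 13/(1 − ρ) + 1, so the effective number of pairs is 13 + (1 − ρ). That is 13.5 at ρ = 0.5 and 13.2 at ρ = 0.8, against 13 under the paired test.

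**The case against.** **Fifteen may mean completers.** The text speaks of subjects studied, not enrolled or randomised, and says that each will receive both interventions. On that reading the 80% is attached to the right number, and replacement of withdrawals would keep it there. This stands as far as it goes: the documents do not show a shortfall. But they do not say completers, and they give no replacement rule.

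**A reader might infer that any missed draw lowers the stated 80%.** The documents do not support this. The power statement is not tied to the ANOVA, and the paired tests on AUC-based kinetics and muscle FSR can usually be run with a draw missing. Deletion of incomplete subjects is not written in the plan either; it follows from the classical form of the method. A percentage of subjects with complete time courses would need an assumed failure rate and independence between draws. That independence is doubtful, since all samples on a study day come through one sampling catheter. No such figure is relied on here.

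**The 80% is itself unsupported.** Its missing inputs are a larger gap than attrition. This is right, and it makes the figures above conditional. It does not alter the direction, nor the loss of about 3 points for the first missing pair.

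**The mixed model does not cure withdrawal.** This also stands, as Step 6 shows. Its value lies in the missed draws.

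**Conclusion.** The point holds in two limited parts.

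First, the 80% is correct only for 15 subjects who supply both study days. It becomes about 77%, 73% and 69% with 14, 13 and 12. These figures rest on taking the 80% at face value, on a two-sided paired t-test and on the back-solved difference of 0.778. The alternative forms of the test move them by less than 2 points.

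Second, the repeated-measures ANOVA has no provision for an incomplete time course, so a missed draw costs the whole subject in that analysis or calls for unplanned imputation. The size of this effect cannot be derived from the documents.

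It would go too far to say that the trial is underpowered as planned. The documents allow the reading that 15 means completers, and they give no loss rate.

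**What to change.** **In the Statistical analysis and power calculations paragraph**, replace the two-way repeated-measures ANOVA for time courses with a linear mixed model. Use fixed effects for intervention, time, their interaction and period, random effects for subject and for visit within subject, and Kenward-Roger or similar small-sample degrees of freedom. Fit it to all available samples. A missed draw then costs one value and not one subject, and visit-1 data from a subject who withdraws are kept. The paired t-tests on summary responses can remain.

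**In the Experimental Overview and Rationale**, state that 80% refers to 15 subjects completing both study days, and give the power at 14, 13 and 12 completers. If withdrawn subjects are to be replaced, say so in the same place.

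**Cost.** Both changes are wording, with a little more analysis work and a slightly less favourable stated power. They add no visit, sample or subject. They do not restore the power lost to a full withdrawal. If the sponsor wants to protect 15 complete pairs, that takes replacement or a larger intake: 15/(1 − loss rate) gives 16, 17 or 19 subjects at assumed losses of 5%, 10% or 20%.

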### Experimental Details:

Participant Selection and Screening: We will study a total of 15 healthy male and females between 60 and 85 years of age. Subjects will not participate in any organized exercise program, or perform any strenuous exercise 72 hours prior to the metabolic experiment.

### Inclusion Criteria:

• Men and women, ages 60-85 years.

Exclusion Criteria:

- Inability to chew meats or difficulty swallowing solid foods
- History of diabetes
- History of malignancy in the 6 months prior to enrolment
- History of gastrointestinal reduction or bypass surgery (Lapband, etc)
- History of a chronic inflammatory condition or disease (Lupus, HIV'AIDS, etc)
- History of chronic kidney disease or currently requiring dialysis.
- Allergy to beef or kiwifruit
- Subjects who do not or will not eat animal proteins
- Subjects who cannot refrain from consuming protein or amino acid supplements during their participation in this study
- Subjects who report regular resistance exercise (more than once per week)
- Hemoglobin less than 9.5mg/dL at the screening visit
- Platelets less than <150,000 at the screening visit

- Subjects who are not willing or able to suspend aspirin for several days prior to their muscle biopsies.
- Subjects who have been prescribed a blood-thinning medication (Coumadin, lovenox, heparin, Plavix, etc).

[figure not shown]
- Concomitant use of corticosteroids (ingestion, injection or transdermal)
- Any other disease or condition that would place the subject at increased risk of harm if they were to participate, at the discretion of the study physician

[figure not shown]
During the screening visit (Day 0), dual-energy X-ray absorptiometry (DEXA) will be performed to determine body composition. This will enable us to normalize data in terms of lean body mass as well as whole body weight. Subjects will be then randomly assigned by a study coordinator to group A or B. Subjects be provided with 2 kiwifruit per day and will be instructed to consume these immediately before their midday meal for two weeks (Figure 3, shaded box) prior to the study. Subjects will also be instructed to abstain from strenuous physical activity for >72 h before the initiation of the metabolic study.

After the first intervention arm, there will be a two-week washout period (Figure 3, dashed box) where subjects are instructed to consume no kiwifruit. After the washout period, the second arm of the study will begin, using the other Kiwifruit.

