phenylalanine) will be started at 4.5 hours and used for the measurement of fibrinogen FSR due to the high turnover rate of fibrinogen Subjects will then eat 2 of either Hort 16A Gold (A) or Hayward Green (B) kiwifruit followed by 100g (cooked weight) ground beef immediately following the second muscle biopsy at T=4.5 hrs. The third muscle biopsy ( $BX_3$ ) will be taken at the end of the study (i.e., at 9.5 hours). The last two muscle biopsies will be used to determine the post-meal muscle protein FSR response. Blood samples will be taken at 0,150, 180, and 270 min before consumption of a test food (the fasted blood samples) and at 290, 310, 330, 360, 390, 420, 450, 480, 510, 540, and 570 min (for fed blood samples) to measure tracer enrichment and plasma responses of amino acids, glucose, and insulin. A total of 15 blood samples will be taken during the study (approximately 90 ml).

Analytical methods. The preparation and subsequent analysis of samples for determination of isotopic tracer enrichment will be carried out by means of gas chromatography-mass spectrometry (GCMS: Models 7890A/5975; Agilent Technologies, Santa Clara CA) as described previously (5, 6). Briefly, 125 ul of 10% sulfosalicylic acid will be added to plasma samples to precipitate protein. Plasma free amino acids will be then extracted from 300 ul supernatant fluid by cation exchange chromatography (Strata-X-C; Phenomenex, Torrance, CA) and dried under Speed Vac (Savant Instruments, Farmingdale, NY). Enrichments of phenylalanine and tyrosine will be measured on the tert-butyldimethylsilyl derivative with the use of GCMS (5, 6). Ions of mass to charge ratios of 234, 235, and 239 for phenylalanine and of 466, 467, 468, and 470 for tyrosine will be monitored with electron impact ionization and selected ion monitoring. Plasma glucose concentrations will be measured spectrophotometrically on a Cobas c 111 analyser (Roche, F. Hoffman-La Roche, Basel, Switzerland). Plasma insulin concentrations will be measured by using commercially available human insulin ELISA kit (Alpco Diagnostics, Salem, MA). Plasma AA concentrations will be determined by using liquid chromatography-mass spectrometry (LCMS: QTrap 5500 MS; AB Sciex) using the internal standard method (6). Preparations of muscle tissue samples obtained from the vastus lateralis muscles will be performed as previously described (5, 6). Phenylalanine tracer enrichment from muscle bound protein will be determined as in plasma analyses.

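### The haemoglobin exclusion limit is printed in mg/dL instead of g/dL, so as written it can exclude nobody

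*Combined protocol and SAP*

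**What the plan says.** The list of exclusions under the Inclusion Criteria heading has two laboratory limits applied at screening. One is "Hemoglobin less than 9.5mg/dL at the screening visit". The next is "Platelets less than <150,000 at the screening visit", which carries no unit at all. Haemoglobin appears nowhere else in the document, so no second statement of the limit, conversion or correction exists.

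The same list ends with a general safety exclusion, left to the study physician, for "Any other disease or condition that would place the subject at increased risk of harm". Participant Selection and Screening describes the population: "We will study a total of 15 healthy male and females between 60 and 85 years of age". The Experimental Overview and Rationale places all study work at one institution.

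The tracer infusion protocol sets muscle biopsies at 2.5, 4.5 and 9.5 hours, and 15 blood samples with a volume of about 90 ml. Each subject goes through both interventions.

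**The concern.** Haemoglobin limits of this size are expressed in grams per decilitre. A limit of 9.5 in milligrams per decilitre lies far below any value a volunteer could have, so the criterion could never be met and would screen out nobody.

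The document does not state the purpose of the limit. It is reasonable to infer that it is meant to keep anaemic people out of a study with repeated blood sampling and needle biopsies in older adults. If so, the protection the authors intended is absent from the text as printed. Eligibility lists are commonly copied into screening forms and used to judge protocol deviations. As printed, a volunteer with a haemoglobin of 9.0 g/dL is not excluded by this line, and turning that person away would need another criterion or a departure from the written limit.

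**Working it through.** **Inputs from the document**

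- Printed limit: below 9.5 mg/dL (exclusion list).
- Number of subjects: n = 15 (Participant Selection and Screening).
- Procedures per infusion day: three biopsies and 15 blood samples (tracer infusion protocol).

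The plan shows no calculation behind the limit, so there is no figure to reproduce. The check is a unit conversion, with 1 g = 1000 mg.

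**Step 1. The printed limit in usual units**

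9.5 mg/dL ÷ 1000 = 0.0095 g/dL.

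**Step 2. The limit evidently meant**

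9.5 g/dL × 1000 = 9,500 mg/dL. The ratio of intended to printed limit is 9,500 ÷ 9.5 = 1000.

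**Step 3. Whether anyone could fall below the printed limit**

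The document gives no haemoglobin range. Assume a deliberately wide range for living adults of 3 to 18 g/dL, which is 3,000 to 18,000 mg/dL.

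- Lowest value: 3,000 ÷ 9.5 ≈ 316 times the printed limit.
- Highest value: 18,000 ÷ 9.5 ≈ 1,895 times the printed limit.
- Even at 1 g/dL: 1,000 ÷ 9.5 ≈ 105 times the printed limit.

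Nobody is excluded under the literal reading. At 9.5 g/dL the limit falls inside the assumed range and works as an anaemia exclusion.

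**Step 4. Procedures the limit would guard**

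The sampling times are 4 fasted and 11 fed, so 4 + 11 = 15 on one infusion day. Over two arms that is 2 × 15 = 30 samples and 2 × 3 = 6 biopsies per subject. If the 90 ml is per infusion day, as the count of 15 suggests, the total is about 2 × 90 = 180 ml.

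**Step 5. How many subjects could be affected**

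The document does not say what share *p* of otherwise eligible volunteers would be below 9.5 g/dL. As an assumption, take 0% to 2%. The expected number is 15*p* and the chance of at least one is 1 − (1 − *p*)^15.

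| Assumed *p* | Expected number of 15 | Chance of at least one |
|---|---|---|
| 0% | 0 | 0% |
| 1% | 0.15 | 1 − 0.99^15 = 14.0% |
| 2% | 0.30 | 1 − 0.98^15 = 26.1% |

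These figures apply only if staff follow the printed unit and no other exclusion catches the person. If staff read g/dL, every entry is zero.

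**The case against.** The best case on the other side is that this is a proofreading matter with no consequence. The literal reading is impossible on its face, so clinical staff would not apply it. The work is done at one institution in people described as healthy, and the study physician can exclude anyone at raised risk. Nothing in the statistical design depends on the line. All of this is fair, and it is why the point is minor.

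The backstops are only partial. The physician's discretion names no haemoglobin value, and a numeric limit exists so that the decision does not rest on case-by-case judgement. The description of subjects as healthy sets no laboratory value either. The platelet, aspirin and blood-thinner exclusions are unaffected by the error, but they address bleeding risk, not anaemia.

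Two further objections also have some force. The 14% and 26% figures rest on an assumed prevalence and on an unlikely reading by staff, so they are conditional upper figures and not a forecast. The text was also read from a PDF, and nearby lines show imperfections such as a stray tag in the platelet bullet. An inserted letter is not a typical reading fault, so an error in the source is more likely, but the text alone cannot rule the other explanation out. A look at the source page settles it.

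**Conclusion.** The concern holds, as a minor point. The haemoglobin limit is wrong as written by a factor of 1000 and, followed literally, excludes nobody. That conclusion rests on the unit conversion and on the assumption that no adult has a haemoglobin near 0.0095 g/dL. It does not depend on the assumed prevalence.

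The likely practical effect is zero, because staff would very probably read g/dL. In the unlikely event of literal use, between 0 and 0.3 of the 15 subjects would be expected to be affected, under the assumed range of 0% to 2%. The trial's endpoints, power and analysis are untouched. What is at stake is the accuracy of an operative eligibility limit that appears intended to protect subjects.

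**What to change.** In the exclusion list, replace mg/dL with g/dL in the haemoglobin line, keeping the number 9.5 and the screening visit as they stand. Have the study physician confirm that 9.5 g/dL is the intended value, and carry the correction into any screening form that copies the criterion.

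The cost is one corrected unit in one line, plus any copies. Sample size, timing and analysis do not change.
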